8.2.6 Study Medication

Table 3: Study Treatments’ shows the Study Treatments and how they will be labelled in all TLF outputs.

Table 3: Study Treatments

Study Treatment	Study Treatment Label
rhNGF 20µg/mL	rhNGF
Vehicle	Vehicle

8.2.7 Efficacy Variables

Primary and Secondary Endpoints: Sande Score

The Symptom Assessment in Dry Eye (SANDE) questionnaire is a short questionnaire to evaluate both dry eye intensity and frequency by using a 100 mm visual analogue scale (VAS). The patient symptoms of ocular dryness and/or irritation will be quantified on the scale based on two questions that assess both severity and frequency of symptoms.

For the assessment, the patients mark on the 100 mm VAS line the point that they feel represents their perception of their current state. The VAS score is determined by measuring in millimeters from the left hand end of the line to the point that the patient marks. The SANDE scores will be then evaluated for the 2 questions severity (0-100) and frequency (0-100).

The Note to File (“NGF0216 Sande Questionnaire Endpoints”, dated 25SEP2017) clarifies the administration instructions of the SANDE questionnaire.

The Sande score will be assessed at Baseline, Week 4, Week 8 and Week 12 visit and is recorded on the eCRF page ‘Symptoms Assessment in Dry Eye’. At each visit, only one assessment is performed aggregating the situation for both eyes (i.e. no separate assessment per study eye).

Primary endpoint will be defined as:

- Change from Baseline in Sande frequency score at Week 8
- Change from Baseline in Sande severity score at Week 8,
i.e. Week 8 score recorded on the eCRF minus the Baseline score on the eCRF

If at least one Sande assessment is missing at Week 8, the values of the last post-baseline assessment (including those from unscheduled visits) with non-missing values for frequency and severity will be imputed (LOCF). No imputation is performed in case of a missing baseline value (as defined in section 8.1).

Additionally, Sande frequency and severity scores as well as respective changes from Baseline will be evaluated without any imputation for Week 4, Week 8 and Week 12, respectively.

Secondary Endpoints: Ocular Surface Staining (NEI Scale)

As grading scale of the corneal and conjunctiva damage, the NEI/Industry Workshop guidelines will be used [2]. The cornea is divided into five sectors (central, superior, inferior, nasal and temporal), each of which is scored on a scale of 0–3, with a maximal score of 15. Both nasally and temporally, the conjunctiva is divided into a superior paralimbal area, an inferior paralimbal area and a peripheral area with a grading scale of 0–3 and with a maximal score of 9 for the nasal and temporal conjunctiva, respectively.

Briefly, on the grading scale used grade 0 reflects normal/healthy situation, whereas grade 3 reflects a severe damage in each considered sector.

Ocular Surface Staining is assessed separately for each eye at Baseline, Week 4, Week 8 and Week 12 visit and is recorded on the eCRF page 'Ocular Surface Staining (NEI score)'.

Corneal Staining will be derived as sum of scores of the five corneal sectors (central, superior, inferior nasal and temporal) ranging from 0 to 15. Corneal Staining will only be calculated, if all 5 sector scores are available.

Conjunctival Staining will be derived as sum of scores of the conjunctival area (nasal-superior paralimbal, nasal-inferior paralimbal, nasal-peripheral, temporal-superior paralimbal, temporal-inferior paralimbal, temporal-peripheral) ranging from 0 to 18. Conjunctival Staining will only be calculated, if all 6 area scores are available.

Both scores will be derived for each eye separately.

Corneal and Conjunctival Staining scores as well as respective Changes from Baseline will be evaluated for Week 4, Week 8 and Week 12, respectively. No imputation will be envisaged for these parameters.

Secondary Endpoint: Tear Film Break-Up Time (TFBUT)

TFBUT will be measured by determining the time to tear break-up. The TFBUT will be measured twice during the first minute after the instillation of the fluorescein. If the 2 readings differ by more than 2 seconds a third reading is taken. The TFBUT value recorded on the eCRF Page 'Tear Film Break Up Time' will be the average of the 2 or 3 measurements.

A TFBUT > 10 seconds will represent normal values, whereas values ≤ 10 seconds are likely for Dry Eyes.

TFBUT is assessed separately for each eye at Baseline, Week 4, Week 8 and Week 12 visit.

TFBUT value as well as respective Changes from Baseline will be evaluated for Week 4, Week 8 and Week 12, respectively. No imputation will be envisaged for this parameter.

Secondary Endpoint: Schirmer Tear Test

Schirmer tear test will be performed to measure aqueous tear secretion prior to the instillation of any dilating or eye drops. Both eyes may be tested at the same time.

While the patient looks upwards, the lower lid will be drawn gently downwards and temporally. The rounded bent end of a sterile strip will be inserted into the lower conjunctival sac over the temporal one-third of the lower eyelid margin. The patients will be instructed to close their eyes gently. After 5 minutes have elapsed, the Schirmer test strip will be removed and the length of the tear absorption on the strip (wetting distance) will be measured (millimeters/5 minutes) and recorded on the eCRF Page 'Schirmer Tear Test'.

A wetting distance of ≥ 10 mm will be considered as normal, whereas lower values indicates a reduced tear secretion.

Wetting distance at 5 minutes is assessed separately for each eye at Baseline and Week 8 visit. Wetting distance at 5 minutes as well as respective Change from Baseline will be evaluated for Week 8. No imputation will be envisaged for this parameter.

Exploratory Endpoint Tear: Matrix Metalloproteinase 9 (MMP-9)

InflammaDry is a rapid, in-office test that detects MMP-9, an inflammatory marker that is consistently elevated in the tears of patients with dry eye disease. Using direct sampling microfiltration technology, InflammaDry accurately identifies elevated levels of MMP-9 protein in tear fluid samples taken from the inside lining of the lower eyelid, the palpebral conjunctiva.

Result of the test will be 'Positive' in case of elevated MMP-9 levels or 'Negative', if no MMP-9 could be detected in the tear fluid. MMP-9 detection is assessed separately for each eye at Baseline and Week 8 Visit. MMP-9 test result at each visit as well as a cross-tabulation of results from Week 8 vs. Baseline will be envisaged for this parameter. No imputation will be envisaged.

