9.1.1 Primary endpoint

- Change from baseline in Symptom Assessment in Dry Eye (SANDE) scores for severity and frequency assessed at 8 weeks of treatment (with LOCF imputation at earlier end of trial assessment)

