9.2 Specific Methods for Efficacy Analyses

As a general principle, all secondary efficacy analyses will be performed for the study eye only. Efficacy data in non-study eye will be listed.

For the primary and secondary endpoints, mean change from baseline will be compared between treatment groups for the study eye. The null hypothesis will be tested that there is no difference between rhNGF and vehicle in the mean overall change from baseline between both treatments:

$$H_0: \mu_{\text{rhNGF}} = \mu_{\text{Vehicle}}$$

$$H_1: \mu_{\text{rhNGF}} \neq \mu_{\text{Vehicle}}$$

Where μ is the mean change from baseline at considered visit within the given treatment.

This hypothesis will be tested exploratory at a 5% level of significance with an Analysis of the Covariance (ANCOVA) with treatment and respective baseline value in the model. The Least-squares means estimate of the treatment effect and the treatment group difference (both with 95% confidence intervals) will be reported. P-values will be rounded to three decimal places. If a p-value is less than 0.001 it will be reported as "<0.001". Due to the high numbers of observations, the assumption of normality is assumed.

The analysis will be performed for the following endpoints:

- Change from Baseline in Sande Frequency and Severity Score at Week 8 (LOCF) for the FAS as exploratory primary efficacy analyses
- Change from Baseline in Sande Frequency and Severity Score at Week 8 (LOCF) for the PPS as supportive to primary efficacy analyses

- Change from Baseline in Sande Frequency and Severity Score (without imputation) at Week 4, Week 8 and Week 12 for the FAS as supportive to primary efficacy analyses
- Change from Baseline in Corneal and Conjunctival staining at Week 4, Week 8 and Week 12 for the FAS as well as PPS as exploratory secondary efficacy analyses
- Change from Baseline in TFBUT at Week 4, Week 8 and Week 12 for the FAS as well as PPS as exploratory secondary efficacy analyses
- Change from Baseline in Wetting Distance (5 minutes) at Week 8 for the FAS as well as PPS as exploratory secondary efficacy analyses.

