9.2.1.2 Handling of Dropouts or Missing Data

In the derivation of endpoints there will be no replacement of missing data except for primary endpoint Change from Baseline in Sande Frequency and Severity Score, age, time since initial diagnosis of Dry Eye disease, adverse event dates as well as concomitant medication dates. Details of applied imputations are described in the respective sections of chapter 8.2.

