10.5 Efficacy Results

10.5.1 Primary Efficacy Analysis

Results of the Sande Frequency and Sande Severity Score at Week 8 (absolute values as well as changes from baseline) will be summarized descriptively by treatment group. For the primary analysis LOCF is applied as described in section 8.2.7. The exploratory p-value and estimates for treatment effect as well as treatment group difference resulting from the ANCOVA analysis specified in section 9.2 will be reported in addition. Primary analysis will be performed on the FAS.

For supportive purposes, this analysis will be repeated for the PPS to investigate the effect of protocol deviations on the results.

A similar analysis will be performed for the Sande Frequency and Sande Severity Score (without imputation) at Week 4, Week 8 and Week 12. Baseline values will also be summarized. This analysis will be performed for the FAS only.

All data on Sande Scores will be listed on the FAS, indicating clearly imputed values.

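### The SAP's LOCF rule is written for the pair of SANDE items, so on its plain reading an observed Week 8 score can be replaced when only the other item is missing

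*SAP*

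**What the plan says.** SAP 8.2.7 lists two primary variables, change in SANDE frequency and change in SANDE severity at Week 8, each defined as "i.e. Week 8 score recorded on the eCRF minus the Baseline score on the eCRF". SAP 9.2 analyses each by ANCOVA with its own baseline value as covariate: "Change from Baseline in Sande Frequency and Severity Score at Week 8 (LOCF) for the FAS as exploratory primary efficacy analyses".

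The imputation rule in SAP 8.2.7 begins "If at least one Sande assessment is missing at Week 8, the values of the last post-baseline assessment (including those from unscheduled visits") and goes on "with non-missing values for frequency and severity will be imputed (LOCF"). The same section says of the questionnaire: "At each visit, only one assessment is performed aggregating the situation for both eyes".

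Other places bear on how to read the rule:

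- SAP 9.2.1.2 says "there will be no replacement of missing data except for primary endpoint Change from Baseline in Sande Frequency and Severity Score", adds a few other variables, and sends the reader to chapter 8.2 for the details.
- Protocol 9.1.1 describes the primary endpoint "with LOCF imputation at earlier end of trial assessment". It has no rule that ties the two items together.
- SAP 4.7, which lists departures from the protocol, does not mention such a rule.
- SAP 10.5.1 says "All data on Sande Scores will be listed on the FAS, indicating clearly imputed values".

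**The concern.** The two items are separate primary variables with separate models, so neither analysis needs the other item. The LOCF sentence nevertheless defines three things on the pair: the trigger (either item missing), the donor (both items present) and what is carried (the values, in the plural). Nothing says that an item observed at Week 8 is kept. Followed as written, a patient who marks one line at Week 8 and leaves the other blank loses the mark that was made.

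Two consequences follow. The primary analysis would use an older score where a real Week 8 score exists. The same patient and item would also have two Week 8 values: the carried one in Table 14.2-1.2 (LOCF) and the recorded one in Table 14.2-2.2 (Observed). The gap between those tables is meant to show the effect of imputing missing scores. Here part of it would come from replacing scores that are not missing.

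**Working it through.** **Step 1: what the trigger counts.** SANDE is completed once per visit for both eyes together, so there are not two questionnaires to count. The phrase about at least one missing assessment can sensibly refer only to the two items. The donor condition, which names both items, fits this.

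**Step 2: apply the rule to example records.** The scores are illustrative and written as (frequency, severity). The pair rule is SAP 8.2.7 as written.

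| Week 4 | Week 8 | Pair rule | Item-by-item LOCF |
|---|---|---|---|
| (55, 50) | (30, missing) | (55, 50) | (30, 50) |
| (55, 50) | (missing, 30) | (55, 50) | (55, 30) |
| (missing, 50) | (30, missing) | no donor; SAP silent on the 30 | (30, 50) |
| (55, missing) | (30, missing) | no donor; SAP silent on the 30 | (30, missing) |
| (55, 50) | (missing, missing) | (55, 50) | (55, 50) |

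In the first row a recorded 30 becomes 55. The baseline cancels, so that patient's change in frequency moves by 55 − 30 = 25 mm. When both Week 8 items are missing and a complete pair exists, the rules agree. They part only when exactly one item is missing.

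**Step 3: the plan's own size figures.** SAP 4.6 gives a difference of 10, SD 20, two-sided alpha 0.05, power 0.8 and 2:1 allocation. With equal arms, n = 2 × (1.960 + 0.842)² × 20² / 10² = 62.8, so 63, which gives the protocol's 94.5 and 47.25. Directly at 2:1, the vehicle arm needs 1.5 × 7.85 × 4 = 47.1, so 48, with 96 active, as the SAP states. With 100 and 50 patients, the standard error of the difference is 20 × √(1/100 + 1/50) = 3.46 mm.

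**Step 4: size of the effect.** The documents give neither a rate of single-item missingness nor a Week 4 to Week 8 shift, so both are assumed.

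- Shift in an arm mean = share with exactly one item missing × mean shift from Week 4 to Week 8. This treats all of those patients as losing the item under study, which is an upper bound for any one item. With 1–5% and 0–10 mm, the range runs from 0 to 0.05 × 10 = 0.5 mm.
- If it happens in one arm only, the treatment difference moves by the same 0–0.5 mm. At most this is 0.5 / 3.46 = 0.14 standard errors.
- If a share p of each arm is affected and the Week 4 difference is a fraction f of 10, the expected difference is 10 × (1 − p(1 − f)). Power below is by normal approximation at 100/50, for f from 0 to 1:

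| p | Expected difference (mm) | Power |
|---|---|---|
| 0 | 10 | 0.823 |
| 1% | 9.90–10 | 0.815–0.823 |
| 5% | 9.5–10 | 0.783–0.823 |
| 10% | 9.0–10 | 0.738–0.823 |

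**The case against.** A reader might infer that the SAP orders an observed score to be overwritten whenever the other item is missing. The documents do not go that far. No sentence says an observed value is discarded. SAP 9.2.1.2 frames LOCF as filling in missing data, and the endpoint is defined from the score recorded at Week 8. Filling only the blank item, from the last complete questionnaire, is a tenable reading. Replacement also needs another post-baseline visit with both items, so it cannot happen in every case. These points stand. They turn the matter into a conflict within the SAP, but they do not settle it, because 9.2.1.2 defers to chapter 8.2, where the pair wording sits.

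The plan also has safeguards. The same ANCOVA is run on Week 8 scores without imputation, the tables are labelled LOCF or Observed, and imputed values are marked in the listing. Missing primary data can lead to exclusion from the per protocol set. The primary endpoint is fully double programmed (SAP 6.3). These would make the problem visible, but they leave the primary FAS estimate as it is. Double programming might expose two readings, but it would not help if both programmers followed the literal text.

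Finally, inference is exploratory and unadjusted, so no confirmatory decision depends on this. The ADaM specifications, table shells and SANDE note to file are separate documents and may already settle the derivation. That cannot be checked here.

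**Conclusion.** The point holds as a defect of specification in the primary variable. On its plain reading, SAP 8.2.7 replaces an observed Week 8 item when exactly one item is missing and another post-baseline visit has both. That conflicts with SAP 9.2.1.2 and with the endpoint definition. The SAP is also silent on the observed item when no complete pair exists.

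The documents do not support a claim that the primary result is materially compromised. On the assumed inputs, the shift is well inside one standard error of the treatment difference. Larger rates of single-item missingness would matter more, but nothing in the documents suggests them on a two-question form. The case for acting rests on the rule's ability to discard valid primary data and on how little the correction costs.

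**What to change.** Replace the LOCF sentence in SAP 8.2.7 with:

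> LOCF is applied separately to each item: if the Week 8 severity (frequency) score is missing, the last non-missing post-baseline severity (frequency) score obtained before the Week 8 visit, including unscheduled visits during treatment, is carried forward. An observed Week 8 score is never replaced.

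The limit to scores before the Week 8 visit is needed because SANDE is also collected at Week 12 and the present sentence sets no upper time limit. Without it, a follow-up score could be carried back. For a patient who leaves before Week 8, the early termination assessment remains eligible, in line with the protocol's endpoint wording.

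Flag imputation per item in the analysis dataset and in Listing 16.2.6-1.1, and check that the ADaM specification agrees.

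The cost is one sentence, a per-item flag and probably a small change to the derivation. The endpoint, model and sample size are unchanged. The change should be made before unmasking.

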8.2.8 Safety Variables

Adverse Events (AE)

AE data are collected on the 'Adverse Events' eCRF page. Corrective medications or procedures due to an AE are documented on the eCRF pages 'Prior and Concomitant Medications' and 'Corrective Procedures Related to AE' respectively.

The AE Description (Investigator term) will be coded to a Preferred Term (PT) and a System Organ Class (SOC) using MedDRA, Version 19.1.

Based on the information provided on the 'Adverse Events' eCRF page, the following definitions will be utilized:

- An ocular event will be identified, if the question 'Is this an ocular event?' is answered 'Yes'.
- An AE with missing severity will be counted as severe.

- A Serious Adverse Event (SAE) is any adverse event where the question ‘Is the event serious?’ has been answered as ‘Yes’. If this question is not answered the event will be considered as ‘Serious’ for analysis purposes.
- *The following adverse events are considered to be of special interest (AESI) and by default shall be reported as SAEs (medically important criteria):*
 - *AEs that caused a decrease in visual acuity of >30 ETDRS letters or > +0.6 LogMAR (compared with the last assessment of visual acuity at the last visit) lasting >1 hour*
 - *AEs that caused a decrease in visual acuity to the level of Light Perception or worse lasting >1 hour*
 - *AEs that required surgical intervention (e.g., conventional surgery, vitreous tap or biopsy with intravitreal injection of anti-infectives, or laser or retinal cryopexy with gas) to prevent permanent loss of sight*
 - *AEs associated with severe intraocular inflammation (i.e., 4+ anterior chamber cell/flare or 4+ vitritis)*
 - *AEs that, in the opinion of the Investigator, may require medical intervention to prevent permanent loss of sight.*

For analysis purposes, and AESI will be identified by ticked box ‘Medically significant or important medical condition’ in the eCRF section ‘SAE criteria’. This means in particular, that all AESIs will be considered as SAEs.

- An AE leading to premature withdrawal of the study treatment is defined as an AE where in the eCRF section ‘Action taken with study treatment’ the boxes ‘Withdrawn’ and ‘Definitely’ are ticked.
- An AE leading to study treatment interruption is defined as an AE where in the eCRF section ‘Action taken with study treatment’ the boxes ‘Withdrawn’ and ‘Temporarily’ are ticked.
- An AE leading to study discontinuation is defined as an AE where in the eCRF section ‘Action regarding Patient’ the box ‘Patient Withdrawn’ is ticked (this should match with the primary reason for early withdrawal of ‘Adverse Event’ on the End of Study eCRF page).
- An AE is classified as ‘Related’ to Study Treatment if the relationship to study medication recorded as ‘Possible’ or ‘Probable’ or ‘Highly Probably’. An AE will be classified as unrelated to study medication if the relationship to study medication was recorded as ‘None’ or ‘Unlikely’. AEs with missing relationship to study treatment will be counted as ‘Related’ to Study Treatment.
- A Fatal AE is defined as an AE where the outcome is recorded as ‘Fatal’.

These definitions will apply accordingly also for the subsequent sub-classes of AEs.

Non Treatment-emergent adverse events (Non-TEAEs)

A Non-TEAE is defined as any AE, which started before the first administration of study treatment. They are identified by the ticked box ‘Before Treatment Period’ in the eCRF Section ‘Did the event occurred.’.

According to the study protocol, both eyes of a patient should be treated. However, there might be the situation, that one eye will not be treated (which will, in fact, be a protocol deviation). For such cases, all ocular events occurring in an eye, which were not treated as indicated on eCRF page 'Study Eye', will also be considered as Non-TEAE irrespective of the timepoint of occurrence.

Treatment-emergent adverse events (TEAEs)

A treatment-emergent adverse event is defined as an AE that started on or after the date of the First Study Treatment Administration. An TEAE will be identified, if

- The eCRF question 'Did the event occurred:' was answered either with 'During Treatment period' or 'During Follow-Up Period'

and

- In case of an ocular event: the affected eye was treated as indicated on the eCRF page 'Study Eye'.

The incidence and frequency of TEAEs will serve as safety endpoint of the study.

TEAEs in the Treatment Period

This will be defined as a TEAE (as defined above) with a start date on or after the date of first study treatment administration and before the Week 8 Visit. It will be identified, if eCRF question 'Did the event occurred:' was answered with 'During Treatment period'.

TEAEs in the Follow-up Period

This is defined as a TEAE (as defined above) with a start date on or after the Week 8 Visit. It will be identified, if eCRF question 'Did the event occurred:' was answered with 'During Follow-Up period'.

For listing purposes, treatment day of onset of AE will be presented according to the definition given in section 8.1.

Missing Codes or Incomplete AE start dates:

In the event that coding information will not be available for a specific AE, the event will be presented as 'Uncodable Event'). However, for final TLFs it is anticipated that all events are coded.

If the eCRF question 'Did the event occur:' was not answered, AEs will be classified to subclass Non-TEAEs, TEAE in the Treatment Period or TEAE in the Follow-up Period based on the AE onset date utilizing the definitions given above (including those for ocular events in untreated eyes). If this is not possible, the event will be classified as TEAE in the Treatment Period.

Missing and/or incomplete AE onset dates will be imputed for calculating relative start and stop days only. Dates will be listed as missing/incomplete [with "-" replacing missing information] but the onset Day listed between square brackets to denote it was calculated based on missing data (i.e. [1]).

Missing and/or incomplete dates will be imputed in a manner that assumes the worst case scenario:

- For a missing start day (but month and year is available), onset is assumed on the first day of the respective month.
- For a missing start month (but year is available), onset is assumed on 1st January of the respective year.
- For a completely missing start date, no imputation will be performed.

If for Non-TEAEs this procedure results in an onset date before date of informed consent, informed consent date will be used.

If for TEAEs during treatment period this procedure results in an onset date before date of first study treatment, date of first study treatment will be used.

If for TEAEs in the Follow-Up period this procedure results in an onset date before date of Week 8 visit, date of Week 8 visit will be used.

Best Corrected Visual Acuity (BCDVA)

Best-corrected visual acuity is measured at all trial visits using standard charts, lighting, and procedures. All eyes must be tested at 4 meters first, even if the refraction was performed at 1 meter. When a patient cannot read at least 20 letters on the chart at 4 meters, the patient is tested at 1 meter.

In addition, the Snellen Equivalent is collected, which is based on smallest line read correctly (i.e. no or max. 1 error). The Scale is categorical and does not easily lend itself to statistical analysis or easy comparison but the logarithm of the minimal angle of resolution (logMAR) scale allows visual acuity to be assessed as a continuous measurement.

In summary, visual acuity is assessed separately for each eye at Baseline, Week 4, Week 8 and Week 12 visit and is recorded on the eCRF page 'Best Corrected Distance Visual Acuity'.

For the analysis, the BCDVA score and the logMAR as well as respective changes from baseline will be evaluated at Week 4, Week 8 and Week 12. No imputation will be envisaged for these endpoints.

The BCDVA score will be derived as the total numbers of letters, which were read correctly at 4 meter plus the total number of letters read at 1 meter as collected on the eCRF page.

When 20 or more letters are read at 4 meters the visual acuity score (i.e. BCDVA score) for that eye is recorded as the number of letters correct at 4 meters plus 30. The patient gets credit for the 30 letters at 1 meter even though they did not have to read them. If no letters are read correctly at either 4.0 meters or 1 meter, then the visual acuity score is recorded as "0."

The logMAR will be derived as $-\log(\text{Snellen Equivalent result})$. For this derivation the Snellen equivalent result is presented as fraction as documented in the eCRF field 'Snellen Equivalent Result'. LogMAR values derived from Snellen equivalent results range from -0.3 (20/10) to 1.6 (20/800) and will be rounded by 2 decimals. An increase in logMAR reflects a worsening of visual acuity.

If for a patient only ability for counting fingers is reported, logMAR will be set to 2; if for a patient only recognition of hand motion is reported, logMAR will be set to 3 [1].

Slit lamp examination

Slit lamp examination is performed separately for each eye at Baseline, Week 4, Week 8 and Week 12 visit and is recorded on the eCRF page 'Slit Lamp Examination (Biomicroscopy)'.

Grading of the eyelids, lashes, conjunctiva, cornea, lens, iris and anterior chamber will be done according to the following scales:

Eyelid - Meibomian glands

- 0 = None (none are plugged).*
- 1 = Mild (1 to 2 glands are plugged).*
- 2 = Moderate (3 to 4 glands are plugged).*
- 3 = Severe (All glands are plugged).*

Eyelid - Erythema

- 0 = None (normal).*
- 1 = Mild (redness localized to a small region of the lid(s) margin OR skin).*
- 2 = Moderate (redness of most or all lid margin OR skin).*
- 3 = Severe (redness of most or all lid margin AND skin).*
- 4 = Very severe (marked diffuse redness of both lid margin AND skin).*

Eyelid - Edema

- 0 = None (normal).*
- 1 = Mild (localized to a small region of the lid).*
- 2 = Moderate (diffuse, most or all lid but not prominent/protruding).*
- 3 = Severe (diffuse, most or all lid AND prominent/protruding).*
- 4 = Very severe (diffuse AND prominent/protruding AND reversion of the lid).*

Lashes

- 0 = Normal*
- 1 = Abnormal*

Conjunctiva – Erythema

- 0 = None (normal).*
- 1 = Mild (a flush reddish color predominantly confined to the palpebral or bulbar conjunctiva).*
- 2 = Moderate (more prominent red color of the palpebral or bulbar conjunctiva).*
- 3 = Severe (definite redness of palpebral or bulbar conjunctiva).*

Conjunctiva - Edema

- 0 = None (normal).*
- 1 = Mild (slight localized swelling).*
- 2 = Moderate (moderate/medium localized swelling or mild diffuse swelling).*
- 3 = Severe (severe diffuse swelling).*
- 4 = Very severe (very prominent/protruding diffuse swelling).*

Lens

- 0 = No opacification (normal lens).*

- 1 = Mild lens opacification.
2 = Moderate lens opacification.
3 = Severe lens opacification.
N/A = Patient with artificial lens

Iris

- 0 = Normal
1 = Abnormal.

Anterior Chamber Inflammation

- 0 = None (no Tyndall effect).
1 = Mild (Tyndall effect barely discernible).
2 = Moderate (Tyndall beam in the anterior chamber is moderately intense).
3 = Severe (Tyndall beam in the anterior chamber is severely intense).

All grading assessments of different eye structures will be evaluated as collected on the eCRF at Baseline Visit, Week 4, Week 8 and Week 12. No imputation will be envisaged for these parameters.

No aggregated presentation is planned for other assessments done during Slit lamp evaluation.

External ocular examination

External Ocular Examination assesses the motility of the extraocular muscles and the appearance and function of the eyelids before the instillation of any dilating or anesthetic eye drops.

Motility of extraocular muscle and appearance/function of eye lids is assessed separately for each eye at Baseline, Week 4, Week 8 and Week 12 visit and is recorded on the eCRF pages 'External Ocular Examination' and 'Appearance and Function of Eyelids'.

For the analysis, the Motility of the Extraocular Muscle will be evaluated by the field of movements Right and up ('Normal', 'Abnormal'), Right ('Normal', 'Abnormal'), Right and Down ('Normal', 'Abnormal'), Left and Up ('Normal', 'Abnormal'), Left ('Normal', 'Abnormal'), Left and Down ('Normal', 'Abnormal') as documented at the eCRF at Baseline Visit, Week 4, Week 8 and Week 12. No imputation will be envisaged for these parameters.

Appearance and Function of Eyelids will be summarized by the following parameters:

- Incidence of proven eyelid deformity/abnormality, which will be considered as present, if the question 'Evidence of eyelid deformity or abnormality' on the eCRF page 'Appearance and Function of Eyelids' is answered 'Yes'.
- Incidence of abnormal motor function of eyelids (i.e. upper lid elevation and forceful lid closure), which will be considered as present, if the question 'Motor function of eyelids' on the eCRF page 'Appearance and Function of Eyelids' is answered 'ABNORMAL'.

- Incidence of corneal exposure in case of closed eyelids, which will be considered as present, if the question 'Is there corneal exposure when the eyelids are closed?' on the eCRF page 'Appearance and Function of Eyelids' is answered 'Yes'.
- Incidence of proven punctal occlusion, which will be considered as present, if the question 'Is there evidence of punctal occlusion?' on the eCRF page 'Appearance and Function of Eyelids' is answered 'Yes'.
- Incidence of punctal plugs, which will be considered as present, if the box 'Punctal plugs' is ticked on the eCRF page 'Appearance and Function of Eyelids'.
- Incidence of thermal or surgical occlusion, which will be considered as present, if the box 'Thermal or surgical occlusion' is ticked on the eCRF page 'Appearance and Function of Eyelids'.
- Incidence of Other punctal occlusion, which will be considered as present, if the respective 'Other' box is ticked on the eCRF page 'Appearance and Function of Eyelids'.

9 Analysis Methods

